5.1.4 Criteria for Termination of the Study (Stopping Rules)

The DMC will conduct ongoing reviews of collected safety data to determine the need for early termination of the study. Stopping rules will be incorporated if any of the following events are identified:

- Decrease in Early Treatment Diabetic Retinopathy Study (ETDRS) best corrected visual acuity (BCVA) of ≥ 15 letters (3-line decrease) unrelated to the natural progression of the disease and determined by the Investigator to be related to the study drug in ≥ 2 subjects
- Intraocular inflammation (anterior or posterior) grade +2 or more in ≥ 2 subjects (using SUN Grading Working Group and Nussenblatt et al grading)
- Increase in intraocular pressure (IOP) to ≥ 30 mmHg for more than 24 hours post-injection in ≥ 2 subjects despite IOP lowering medication treatment
- Any other serious ocular or systemic adverse event (AE) that, in the opinion of the Investigator, is related to the study drug in ≥ 1 subject

Upon DMC's recommendation for study termination, further enrollment of study subjects in the study will be discontinued. Subject withdrawal procedures must be followed for all active subjects to ensure the safety of the subjects at the conclusion of the study.

5.2 Selection and Withdrawal of Study Subjects

Approximately 18 subjects may be enrolled into the study, with 6 subjects in each of the low (Group 1), mid (Group 2), and high (Group 3) treatment dose arms. The first 9 sequential subjects MUST NOT be treatment naïve. The additional 9 subjects can be previously treated or treatment naïve.

5.2.1 Subject Inclusion Criteria

1. 18 years of age or older
2. Type 1 or 2 diabetes mellitus with study eye center-involved DME and with central subfield thickness ≥ 305 μm (females) or 320 μm (males) on Spectralis[®] Spectral Domain Optical Coherence Tomography (SD-OCT) device or 290 μm (females) or 305 μm (males) on Cirrus[®] SD-OCT device and intraretinal or subretinal fluid as evidenced by Spectral Domain Optical Coherence Tomography (SD-OCT) at Screening, as confirmed by the Investigator
3. BCVA in the study eye at Baseline (Day 0) between 65 and 23 ETDRS letters (20/40 and 20/320 Snellen equivalent) with BCVA decrement determined by the Investigator primarily attributable to DME
4. BCVA of 34 ETDRS letters or better (20/200 or better Snellen equivalent) in the non-study eye at Baseline (Day 0)
5. Able and willing to give signed informed consent and follow study instructions

5.2.2 Subject Exclusion Criteria

1. Any signs of high risk proliferative diabetic retinopathy in the study eye and related complications, as determined by the Investigator
2. Previously treated patients who are non-responders to anti-VEGF determined by the Investigator
3. Panretinal photocoagulation within 6 months or macular laser photocoagulation within 3 months from Screening in the study eye

4. Use of intraocular or periocular corticosteroids within 4 months (with the exception of fluocinolone acetonide intravitreal implant which is excluded), Aflibercept within 8 weeks, Ranibizumab and Bevacizumab within 6 weeks from Baseline (Day 0) in the study eye
5. Any concurrent disease that would require medical or surgical intervention during the study in the study eye (e.g. retinal detachment, significant cataract, uncontrolled glaucoma)
6. Any condition that may preclude improvement in visual acuity or affect the evaluation of the study eye after resolution of DME (e.g. vitreous hemorrhage, macular ischemia, pre-retinal fibrosis involving the macula, pre-retinal macular hemorrhage, visually significant vitreomacular traction, or media clarity insufficient to obtain quality images)
7. Chronic uveitis or ongoing clinically significant infection or inflammation (e.g. keratitis, scleritis) in either eye
8. Previous vitreoretinal surgery, previous filtration surgery, cataract surgery within 3 months or YAG laser capsulotomy within 1 month of Screening in the study eye
9. History of cataract surgery complications (vitreous loss) or aphakia in the study eye
10. History of penetrating ocular trauma in the study eye
11. History of allergy to fluorescein or povidone iodine
12. History or current systemic condition that preclude the safe administration of the study treatment or confound results (e.g. HbA1c > 12% at Screening, uncontrolled hypertension [\geq 180/100] on optimal medical regimen at Screening, systemic anti-VEGF treatment, renal failure requiring dialysis, or renal transplant)
13. Women of childbearing potential who are pregnant, nursing, planning a pregnancy, or not using a medically acceptable form of birth control
14. Participation in an interventional clinical study at Screening

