In addition to VEGF inhibition, Tie2 (Tyrosine kinase with immunoglobulin-like and epidermal growth factor-like domains 2) is also being increasingly recognized for its role in regulating vascular permeability. Tie2 is a tyrosine kinase receptor that, like VEGF receptor-2, is located on vascular endothelial cells and has been implicated in the modulation of vascular permeability (Wong 1997, Thurston 1999, Thurston 2000). However, although phosphorylation of VEGF receptor-2 stimulates vascular leakage, phosphorylation of Tie2 activates downstream pathways that suppress vascular leakage and promote vascular stabilization. Angiopoietin 1 is an endogenous full agonist that stimulates phosphorylation of Tie2 (Davis 1996). Angiopoietin 2 is an endogenous weak, partial agonist that competes with angiopoietin 1, thereby suppressing Tie2 phosphorylation (Maisonpierre 1997, Yuan 2009). Tie2 is also regulated by vascular endothelial protein tyrosine phosphatase (VE-PTP), also known as human protein tyrosine phosphatase beta, which is physically associated with Tie2. It dephosphorylates Tie2, thereby reducing Tie2 activation and signaling through the Tie2 pathway (Yacyshyn 2009). Levels of both angiopoietin 2 and VE-PTP are increased by hypoxia, leading to accentuated VEGF-mediated ocular neovascularization and vascular leakage (Hackett 2000, Hackett 2002, Oshima 2004, Oshima 2005, Shen 2014). Preclinical models have shown that VE-PTP inhibition, even in the presence of high angiopoietin 2, restores Tie2 activation (Shen 2014).

The drugs currently used to treat DME are administered IVT and they have a short duration of action; Lucentis® is administered every month and Eylea® is administered monthly initially, and if there is an adequate response it may be dosed every 2 months or administered every 3 months. Frequent dosing is a burden for patients and can also increase the chance of adverse effects related to the injection. Thus, there is a considerable unmet medical need for alternative

treatment options with prolonged treatment duration to reduce treatment burden and new mechanism of action for patients who could not achieve optimal treatment effect from anti-VEGF agents.

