5.1 Overall Study Design

This is an open-label, dose-escalating, 48-week study assessing the safety, tolerability, bioactivity and duration of action of a single intravitreal injection of 0.1 mg (low dose), 0.25 mg (mid dose), or 0.5 mg (high dose) AXT107 in approximately 18 subjects (6 subjects per dose) with DME.

Upon providing written informed consent, subjects will be enrolled into the study with the dose-escalation strategy as depicted in [Figure 1](#). A total of 16 visits are planned in the study, including Screening (Day -14 to -1), Baseline (Day 0), and follow-up visits on Day 1 (Phone call), Week 1, Week 4, Week 8, Week 12, Week 16, Week 20, Week 24, Week 28, Week 32, Week 36, Week 40, Week 44 and Week 48. [Table I-1](#) in [Appendix I](#) provides a summary of the study visit and the procedures to be performed at each visit.

The study drug will be administered by the study Investigator at Baseline (Day 0), after completion of the Baseline assessments, including BCVA, IOP measurement, slit lamp biomicroscopy, and SD-OCT. IOP will be repeated and DFE will be completed after administration of the study drug at the Baseline visit. Post-baseline assessments will be completed as specified in Section 7 and as described in the Manual of Procedures (MOP).

Figure 1 Study Schematic

¹ DMC review of safety data at Week 1. Three subsequent subjects are to be enrolled to receive the next higher treatment dose only upon confirmation from the DMC of acceptable safety profile of the previous group.

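### Exclusion 4 has no catch-all for unlisted intravitreal drugs and exclusion 14 has no look-back, so carry-over from a recent treatment could enter the AXT107 bioactivity results (minor)

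*Combined protocol and SAP*

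**What the plan says.** Section 5.2.2 of the protocol, repeated in the synopsis, holds every eligibility rule on prior treatment.

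- **Exclusion 4, corticosteroids:** "Use of intraocular or periocular corticosteroids within 4 months", with the fluocinolone implant excluded without a time limit.
- **Exclusion 4, anti-VEGF drugs:** "Aflibercept within 8 weeks, Ranibizumab and Bevacizumab within 6 weeks from Baseline (Day 0) in the study eye". No other intravitreal agent is named and no general phrase follows.
- **Exclusion 14, other trials:** "Participation in an interventional clinical study at Screening". It states no period before Screening.
- **Exclusion 3, laser:** "Panretinal photocoagulation within 6 months or macular laser photocoagulation within 3 months from Screening in the study eye". Exclusion 8 sets similar rules for eye surgery.
- **Exclusion 12, systemic conditions:** its examples include "systemic anti-VEGF treatment, renal failure requiring dialysis, or renal transplant".

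Section 5.1 places Screening 1 to 14 days before the injection. Section 5.3.4 prohibits no concomitant medication. Section 5.1.2 states that there is no randomization or masking, and the synopsis lists no control product. Section 6.3 summarizes change from baseline in CST and BCVA by dose level, with no split or adjustment for prior treatment.

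**The concern.** The sponsor wrote washouts because an earlier intravitreal drug can disturb what is measured after Day 0. The same reasoning applies to an intravitreal drug that is not on the list and to an investigational drug from another trial, but the rules reach neither. The documents give no reason for stopping at the named drugs.

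The secondary objective, bioactivity and duration of action, is at stake. Without a concurrent control, all change in CST and BCVA after Day 0 is read as the effect of AXT107. Part of it could be the course of an earlier drug. Under section 5.3.3, rescue from Week 12 can be triggered by a rise in CST over the lowest previous visit. A fading earlier effect could therefore contribute to rescue and be taken for short AXT107 duration. With about 6 eyes per dose, one eye has visible weight in a dose-level mean.

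**Working it through.** The plan gives no figure to reproduce on this point. Section 6.4 says that the sample size has no statistical basis, and section 6.2 defines no hypotheses. The check has three parts: the eligibility text, the direction of bias, and the weight of one eye.

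**1. Does any rule stop such an eye?** Take eye A, recently given an intravitreal drug that exclusion 4 does not name. Take eye B, recently given an investigational intravitreal drug in a trial that the subject left before Screening.

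- Exclusion 4: neither drug is named, so neither eye is excluded.
- Exclusion 14: eye A was in no trial. Eye B's trial had ended for that subject by Screening. Neither is excluded.
- Exclusions 3 and 8: laser and surgery only.
- Exclusion 6: eye conditions, not prior drugs.
- Exclusion 12: systemic conditions, including systemic anti-VEGF treatment. It does not reach an intravitreal drug.
- Section 5.3.4: no medication is prohibited.
- Inclusion 2: CST above threshold with fluid. This stops an eye whose edema is fully suppressed at Screening. Table I-1 has eligibility reviewed again at Baseline, but inclusion 2 itself is worded for Screening.

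Both eyes can be enrolled if edema is present at Screening. A subject who left a trial just before Screening could be dosed 1 to 14 days after the Screening visit.

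**2. Which way would carry-over act?** Let P(t) be the amount by which the earlier drug lowers CST at time t after Day 0. The endpoint is change from Day 0, so the carry-over in one eye's CST change is

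carry-over = −[P(t) − P(0)].

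- P(t) = P(0), stable effect: carry-over is 0, because the effect is already in the baseline.
- P(t) > P(0), effect still growing: CST falls further and AXT107 is flattered.
- P(t) < P(0), effect wearing off: CST rises and AXT107's effect or duration is understated.

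**3. How much does one eye weigh?** Section 6.4 gives 6 subjects per dose. With n = 6 and a carry-over of c µm in one eye, the group mean moves by c/n. The documents give no value for c, so 50 to 200 µm is an assumed range.

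- Share of the group: 1/6 = 16.7%.
- c = 50: 50/6 = 8.3 µm.
- c = 100: 100/6 = 16.7 µm.
- c = 200: 200/6 = 33.3 µm.
- One eye that changes responder status moves a BCVA responder percentage by 100/6 = 16.7 points.

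**The case against.** The strongest case for the plan has four parts.

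- **Active edema is required.** Inclusion 2 asks for thick CST and fluid no more than 14 days before dosing. This makes full suppression at entry unlikely, and that much stands. It does not exclude a partial effect that is changing, or a drug given so recently that its effect has yet to develop.
- **The gap may seldom be used.** Section 3.1 names two products as current DME drugs, and exclusion 4 covers the active agents of both. A subject recently dosed in another trial may still be in its follow-up, and so caught by exclusion 14. This also stands: the gap is confined to unlisted agents and to trials already exited, and its frequency cannot be judged from the documents.
- **The study is descriptive.** Safety is the primary objective and there are no hypotheses. This limits the consequence and is why the point is minor.
- **History is already collected.** Table I-1 takes ophthalmic history at Screening, and section 6.3 lists medical history, ocular procedures and concomitant medication. No listing is said to set time since the last injection beside a subject's outcome.

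A reader might also draw three stronger conclusions. The documents do not support them.

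- **That the 8-week aflibercept washout contradicts section 3.1.** That section says "if there is an adequate response it may be dosed every 2 months or administered every 3 months". Eight weeks agrees with the first interval in the sentence. A dosing interval is also not a duration of effect, and inclusion 2 requires the eye to have active edema. Subtracting 8 weeks from 3 months does not show how long residual effect lasts after Day 0.
- **That carry-over falls mainly on the early cohort**, because "The first 9 sequential subjects MUST NOT be treatment naïve". Those subjects face the same washouts as everyone else, and nothing shows that they received unlisted drugs.
- **That any residual drug flatters AXT107.** A stable effect cancels in change from Day 0, and a fading one works against AXT107.

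**Conclusion.** The gap is in the text and no other section closes it. The rules admit an eye recently given an unlisted intravitreal drug, or an investigational one in a trial already exited, to an uncontrolled change-from-baseline study. The resulting bias can go either way and bears on the secondary bioactivity and duration objective.

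One affected eye is 16.7% of a 6-eye group. It would move the group mean CST by about 8 to 33 µm if its own change were shifted by 50 to 200 µm. That range is an assumption, and so is the presence of an affected eye: the documents do not show whether there would be none, one or several. The text supports a possible bias, not an expected one. Severity is minor.

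**What to change.** 1. **Exclusion 4:** add wording that covers any other intravitreal agent, licensed or investigational, given to the study eye before Day 0.
2. **Exclusion 14:** keep the rule on participation at Screening and add a look-back for prior investigational ocular treatment.
3. **Intervals:** the sponsor sets them on clinical grounds. None is proposed here.
4. **Listing (section 6.3):** give the last study-eye drug and the weeks from that injection to Day 0 beside each subject's CST and BCVA course. This is worth doing even if enrollment is complete, because it lets a reader see whether an unusual course follows a recent treatment.

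The cost is two eligibility sentences, changed in both section 5.2.2 and the synopsis, and an addition to one listing. The downside is that a few candidates recently treated with an unlisted or trial drug would wait or not be enrolled.

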5.2.3 Subject Withdrawal Criteria

Subjects may withdraw from participation (withdraw consent) at any time during the study, without cause, and regardless of circumstances. In addition, the Principal Investigator or the Medical Monitor may terminate a subject's participation in the study for reasons related to safety and/or to protect the rights and interest of the subject. Subjects may be discontinued from the study due to any of the following reasons:

- Non-compliance
- Lost to follow-up
- Protocol violation
- Withdrawal by subject
- AEs
- Death
- Clinical judgment of the Investigator or the Medical Monitor
- Other

If a subject is discontinued from the study before completing the Week 48 visit, all safety and performance assessments scheduled at the final visit should be performed on the day of discontinuation, to the extent possible. The final assessments and the reason for discontinuation should be documented in the subject's records and the appropriate early termination Case Report Forms (CRF).

Subjects who prematurely discontinue from the study may be replaced only with approval obtained from the Sponsor.

5.3 Treatment of Subjects

5.3.1 Study Drug Administration

Study medication will be administered via IVT injection by a qualified physician. Subjects will receive a single dose of AXT107 (based on assigned dosage) in the study eye on Day 0 (Baseline). Refer to the Pharmacy Manual for instructions on the preparation of the study drug.

5.3.2 Determination of the Study Eye

Study eye will be defined as the eye that meets all of the inclusion and none of the exclusion criteria. If both eyes meet criteria, study eye will be defined as the eye with the worse vision on Day 0 (Baseline). If both eyes have the same vision, the right eye (OD) will be determined as the study eye. Refer to the MOP for study eye preparation prior to administration of study drug.

5.3.3 Rescue Therapy

Rescue therapy with the Investigator's preferred treatment will be allowed starting at Week 12, for any subject who has received injection of AXT107 and for whom there is ≥ 7 letter ETDRS BCVA decrease from Baseline (Day 0) or $\geq 75 \mu\text{m}$ increase in CST compared to the lowest measurement at any previous visit. It is recommended that rescued subjects complete all study follow up visits through Week 48/Exit.

5.3.4 Concomitant Medication

There are no prohibited concomitant medications in the study. When possible, concomitant medications should be used with a consistent dose throughout the study. The use of concomitant medications (prescription or over-the-counter) will be recorded in the source documents during the study, using the generic name, indication, route of administration, frequency, dose, start date and stop date (if applicable).

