6. STATISTICAL ANALYSIS PLAN

6.1 Analysis Populations

Intent-to-Treat (ITT) Population:

The ITT population will include all subjects who have received study medication. This population will be the primary population for efficacy analyses and will be used to summarize all efficacy variables.

Safety Population:

The safety population will include all subjects who have received study medication. This population will be used to summarize safety variables and will summarize subjects as treated.

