6.3 Statistical Methods

Age, sex, race, ethnicity, and baseline assessments will be summarized and listed by dose level. Medical history, history of ocular surgery and procedures, and concomitant medication will also be summarized and listed.

Changes from baseline in BCVA and retinal thickness (CST) will be summarized by dose level using continuous summary statistics. BCVA change will be summarized using categorical summaries as well, including frequency counts and percentages improving at least 5, 10, and 15 letters.

Verbatim descriptions of AEs will be mapped to MedDRA thesaurus terms and be presented in a data listing. Treatment emergent AEs, those that occur after the first dose of study medication, will be summarized by dose level using frequency and percent for each system organ class (SOC) and preferred term (PT) within each SOC. Summaries will be presented separately for ocular and non-ocular AEs. TEAEs will be summarized by severity and study drug relatedness.

BCVA will be summarized at each time point using both continuous summaries (ETDRS letter score), including change from Baseline (Day 0), and categorical summaries, including change from Baseline (Day 0) on an ETDRS chart in the number of lines.

IOP will be summarized at each time point using both continuous summaries, including change from Baseline (Day 0), and categorical summaries for pre-stated categories of change in IOP.

Slit lamp biomicroscopy and ophthalmoscopy measures will be summarized at each measured time point using categorical summary statistics.

FA will be summarized by visit.

DRSS will be summarized by visit and change from Baseline (Day 0) to each visit.

Vital signs will be summarized at each visit and for change from Baseline (Day 0) to each visit using continuous summary statistics by treatment group and visit.

Clinical laboratory results will be summarized using both continuous summaries, including change from Baseline (Day 0), and discrete summaries, including frequency and percent of subjects with an abnormal value and shift tables from Baseline (Day 0). Additionally, laboratory data will be presented in data listings.

Exploratory analyses will be performed to summarize the results obtained from the Notal Vision Home OCT device and home M&S® Technology visual acuity measurement.

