6.5 Handling of Missing Data

For safety measures, missing scores will not be imputed for data summaries. Completely or partially missing onset and resolution dates for AEs and completely or partially missing start and end dates of concomitant medications will be imputed in a conservative fashion. For bioactivity endpoints, missing post-treatment values will be imputed using the last-observation-carried-forward (LOCF) approach.

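### Section 6 has no rule for CST and BCVA values observed after rescue, so by default they enter the by-dose summaries as if they were AXT107 effect

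*Combined protocol and SAP*

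**What the plan says.** **Rescue.** Section 5.3.3 states: "Rescue therapy with the Investigator's preferred treatment will be allowed starting at Week 12". The trigger is a loss of 7 or more letters from Baseline, or a CST rise of 75 µm or more over the lowest value at any previous visit. On follow-up it says: "It is recommended that rescued subjects complete all study follow up visits through Week 48/Exit".

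**Other treatment.** Section 5.3.4 states: "There are no prohibited concomitant medications in the study". It asks that medications be recorded by name, indication, route, frequency, dose and dates. The washouts for anti-VEGF, corticosteroid and laser in section 5.2.2 look back from Baseline or Screening only.

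**Analysis.** Section 6.1 defines the ITT population as everyone dosed and says: "This population will be the primary population for efficacy analyses and will be used to summarize all efficacy variables". Section 6.3 says: "Changes from baseline in BCVA and retinal thickness (CST) will be summarized by dose level using continuous summary statistics", and then: "BCVA change will be summarized using categorical summaries as well, including frequency counts and percentages improving at least 5, 10, and 15 letters". Section 6.5 says: "For bioactivity endpoints, missing post-treatment values will be imputed using the last-observation-carried-forward (LOCF) approach". The only planned output that would show other treatment is general: "Medical history, history of ocular surgery and procedures, and concomitant medication will also be summarized and listed".

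Section 6 does not mention rescue. It has no flag, no rule for values after rescue, no non-responder rule, and no count of, or time to, rescue.

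**The concern.** The secondary objective (section 4) is the bioactivity and duration of action of AXT107, which is given once. Section 6 defines no separate duration measure, so duration can be read only from CST and BCVA by visit.

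A subject who meets the 5.3.3 trigger is one in whom the effect has been lost or never appeared. If the rescue works, that subject's later CST and BCVA improve and are averaged into the dose group. With no control arm and no masking, nothing in the design separates that gain from an AXT107 effect.

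The plan also treats similar subjects differently. A rescued subject who stays contributes post-rescue values. One who leaves when rescue is needed contributes the pre-rescue value through LOCF. One who is rescued, improves and then leaves has a post-rescue value carried forward to Week 48.

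At stake is the reading of how long a single injection lasts, including at the interims after Weeks 24 and 36. If rescue differs between doses, the dose comparison is affected too.

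**Working it through.** **Plan's own figure.** Section 6.4: 3 doses × 6 subjects = 18, which agrees with the stated total. No power calculation applies, because section 6.2 defines no hypotheses and section 6.4 says the size has no statistical basis.

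**Visits that can carry post-rescue values.** Section 5.1 lists 16 visits. Removing Screening, Baseline and the Day 1 phone call leaves 16 − 3 = 13 in-clinic post-baseline visits. A rescue at the Week 12 visit is followed by Weeks 16 to 48 every 4 weeks: (48 − 16)/4 + 1 = 9 visits, and 9/13 = 69%. This is the maximum; later rescue affects fewer visits.

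**Which rule applies to a post-rescue value.**
- It is observed, so LOCF (6.5) does not replace it.
- The subject was dosed, so 6.1 keeps the subject in every efficacy summary.
- 6.3 summarizes change by dose with no exception.

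Retention therefore follows from silence, not from an explicit instruction.

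**Weight of one subject.** Shift in the dose mean = (rescued subjects / 6) × (change after rescue). For one rescued subject, taking the trigger value as the comparison:

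| Change after rescue (assumed) | Shift in dose mean |
|---|---|
| BCVA −7 to 0 letters | 7/6 = 1.17 letters |
| BCVA −7 to +5 letters | 12/6 = 2.0 letters |
| CST, half of the 75 µm rise reversed | 37.5/6 = 6.25 µm |
| CST, all of the 75 µm rise reversed | 75/6 = 12.5 µm |

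One subject crossing a responder threshold moves that percentage by 1/6 = 16.7 points. Recovery from −7 only to Baseline does not do this; a 12-letter gain to +5 does, for the 5-letter category.

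**Illustration with 2 of 6 rescued (all values assumed).** Non-rescued eyes: −50 µm and +3 letters. Rescued eyes: +25 µm and −7 letters before rescue, −100 µm and +5 letters after.
- CST, post-rescue values kept: (2 × −100 + 4 × −50)/6 = −66.7 µm.
- CST, last pre-rescue value used: (2 × 25 + 4 × −50)/6 = −25.0 µm.
- BCVA, post-rescue values kept: (2 × 5 + 4 × 3)/6 = +3.7 letters.
- BCVA, last pre-rescue value used: (2 × −7 + 4 × 3)/6 = −0.3 letters.

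The assumed response here (125 µm, 12 letters) is larger than the trigger amounts, so this shows how the two summaries can diverge and is not a forecast.

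**How likely a group is to be affected.** The documents give no rescue rate. The chance of at least one rescued subject in a group of 6 is 1 − (1 − p)^6. For assumed p of 10%, 30% and 50% this is 47%, 88% and 98%.

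**The case against.** The strongest reply is that this is an open-label, descriptive study of about 18 subjects with a safety primary objective and no hypotheses. Summarizing all observed data in all dosed subjects is a recognised treatment-policy choice. That stands in part: no test result or error rate is at risk, and the all-observed tables should stay. But the stated interest is a single injection's duration, and those tables alone describe AXT107 followed by whatever else was given.

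A second reply is that the concomitant-medication listing will show who was rescued. It will show drugs, but it does not separate the values that follow them. Laser rescue is a procedure rather than a medication, and the recording fields in 5.3.4 do not name the eye. The case report form is not available here, so the eye may be captured elsewhere.

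Three stronger readings are tempting, and the documents do not support them.
- *5.3.4 lets investigators treat the study eye for DME at any time.* Section 5.3.3 is the specific rule, with a start week and criteria. Earlier or off-criteria use is best read as a deviation to be documented under 7.1. The wording of 5.3.4 deserves a clarification, no more.
- *The bias can only grow at later visits.* The number of rescued subjects accumulates, but section 3.1 describes current DME drugs as short acting, so one eye's contribution can shrink again.
- *The per-subject shifts are minimum biases.* They compare with an eye held at its trigger value. An unrescued eye might partly recover. Section 3.1 also says anti-VEGF is insufficient in 40 to 60% of patients, and exclusion 2 removes only previously treated non-responders.

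**Conclusion.** The concern holds for rescue under 5.3.3. Followed as written, the plan puts post-rescue CST and BCVA into the only outputs from which single-injection duration can be read, at up to 9 of 13 in-clinic post-baseline visits.

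The direction tends to favour AXT107, on the assumption that rescue is effective on average. That is reasonable: section 3.1 calls VEGF neutralization first-line treatment, and previously treated non-responders are excluded. The size cannot be estimated without a rescue rate. The firm part is the leverage: each subject is one sixth of a dose mean, so full reversal of a trigger amount is worth about 1.2 letters or 12.5 µm. Distortion between doses requires rescue, or its effect, to differ by dose.

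The harm is a possibly misleading description on a secondary objective. The plan should be changed, but the primary safety objective is not affected.

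**What to change.** **In 6.3:**
- Flag the first study-eye DME treatment after the AXT107 injection, whether drug, laser or other procedure, with eye and date.
- Keep the all-observed summaries. Beside them, present CST and BCVA summaries in which values after that treatment are replaced by the last value before it. This is in keeping with the LOCF approach of 6.5.
- In those added summaries, count treated subjects as non-responders from that point for the 5-, 10- and 15-letter percentages.
- Report the number treated by dose and visit, and time to first rescue by dose. The latter is the most direct measure of duration available.

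**In 5.3.4, as a minor clarification:** state that study-eye DME treatment (intraocular or periocular drug, or laser) is given only as rescue under 5.3.3, and that any earlier or off-criteria use is documented as a deviation.

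**Cost.** One flag, eye and procedure fields if the case report form lacks them, and one extra set of descriptive tables. Sample size and access to rescue do not change. Duration may look less favourable. Carrying a value forward can overstate duration if a still-improved eye is treated; the all-observed tables and rescue counts will show this. An eye rescued on CST while its vision is still improved would carry that gain in the BCVA mean yet count as a non-responder, so a table footnote should state both conventions.
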